## 3.2 Secondary Objectives

Secondary objectives of this study are as follows.

- To assess the effect of CBD upon plasma CBD and THC levels when administered to patients with AUD+PTSD/subthreshold PTSD. We predict that within-group plasma CBD levels will stabilize within one week, i.e. 45 minutes post-CBD dosing levels obtained after 1 week of treatment will not differ from those obtained after 4 weeks of treatment.
- 2) To contrast the effects of CBD to those of placebo on psychological and cognitive domains relevant to AUD and PTSD/subthreshold PTSD. Relative to placebo, we predict that CBD will improve self-report measures of craving, anxiety, mood, and self-efficacy, and improve cognitive function. We will also specifically target the domain of traumatic stress induced craving using a human laboratory task. We predict that relative to placebo, CBD will lead to a greater attenuation in subjective traumatic stress and alcohol cue-induced craving and accompanying physiological stress response.
- 3) To assess the effect of CBD on plasma anandamide levels. We will contrast levels of plasma anandamide between samples taken at baseline and after CBD treatment, and between samples taken at predicted preand 45 minutes post-dosing CBD levels. We predict that relative to placebo, CBD will lead to an increase in plasma anandamide between these time points.
- 4) To assess the temporal relationship between the onset in reduction of PTSD symptoms and the onset in reduction of AUD symptoms. We predict that a reduction in PTSD symptoms will precede a reduction in

Exploratory Aim 1: To examine voicemarkers as a function of a patient's AUD and PTSD status and to develop assessment models that use lexical and prosodic features to classify a patient's AUD and PTSD status.

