# 3 Study Enrollment and Withdrawal

# 5.1 Inclusion Criteria

In order to be eligible to participate in this study, an individual must meet all of the following criteria:

- 1. Males and females age 18-70
- 2. DSM-5 diagnosis of moderate or severe AUD

3. DSM-5 diagnosis of PTSD with Clinician Administered PTSD Scale (CAPS-5) OR subPTSD diagnosis (meeting criterion A, F, G, H and at least 6 symptoms across any criteria B-E) with Clinician Administered PTSD Scale (CAPS-5)

4. Able to provide voluntary informed consent

5. At least 4 heavy drinking days (4 or more drinks per day for a woman, 5 or more drinks per day for a man) in the 30 days prior to screen

6. If of childbearing potential (male or female), are willing to use approved form of contraception from screening for duration of the trial

- 7. Able to provide at least two locators
- 8. Endorse desire to cut down or stop drinking
- 9. Agrees to abstain from all other cannabinoid use for the duration of the study
- 10. Confirms they are reliably domiciled

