# 7 Study Procedures and Schedule

# 7.1 Study Procedures/Evaluations

## Inclusion/exclusion criteria:

Medical screening by an NP or MD will include medical history and physical exam, liver function tests, complete blood count, urinalysis, menstrual calendar (if female except those menopausal for >1 year since last menstrual period and/or had a bilateral oophorectomy), pregnancy test (if female except those menopausal for >1 year since last menstrual period, had a hysterectomy, and/or had tubal ligation), and vital signs for safety. The licensed provider (NP or MD) will also review participants' controlled substance prescription history using the online Prescription Monitoring Program (PMP) Registry to inform study eligibility. The Structured Clinical Interview for DSM-5 (SCID ) will be used to determine substance use disorder diagnoses and exclusionary psychiatric disorders {First, 1997 #114}. The Life Events Checklist (LEC) and Clinician Administered PTSD Scale (CAPS) for DSM 5 will be used to assess PTSD symptoms [101]. The Concussion Symptom Inventory (CSI) and a modified version of the Ohio State University TBI Identification Method (TBI OHIO) will be used to assess for Traumatic Brain Injury (TBI). The clinical interviews will be conducted by SCID and CAPS trained study clinicians, masters-level study team members and bachelors-level study team members with sufficient psych-assessment training as approved by the study PI. Individuals will have the option to be audiotaped during the screening interview. If the participant consents, audio recordings will be used to ensure quality control and clinical adherence to the protocol. Audio recordings will also be used for voice-marker analysis. If a participant voices that he/she is uncomfortable with the audiotaped interview, he/she can tell a study team member that he/she does not wish to participate in this component of the study. In that case, the participant could still participate in the study but would not complete the audiotaped interview.

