#### 7.2.4 Data Storage and Sharing of Voice-markers Data

Only the investigator and authorized study personnel will have access to the digital audio recordings to ensure quality control, clinical adherence during calibration and to study voice-markers. Under no circumstances will any unauthorized personnel listen to or view the tapes without the written permission of the participant.

The study team will collect speech data from audio recordings collected from the clinical interview at the screening visit. The digital audio recordings will then be transferred for analysis via encrypted CDs or secure NYU sites and stored on secure servers. All the recordings will be de-identified and labeled with a unique study code number for each participant in the study. The study team will identify a professional, specialized entity to conduct the voice-markers analysis; any authorized entity will only receive de-identified data without any PHI or linking information and will store the data on secure servers.

No individual identities will be used in any reports or publications resulting from the study. Study information, such as the digital audio recordings will be coded with a code number unique to the study. Only authorized

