#### #S17-00949

NYUMC study personnel, with the permission of the principal investigator, will have access to the files that links the identifying information and study ID codes. Digital audio recordings of interviews will be encrypted and pass-code protected while retained on a secure NYU server until the conclusion of the study; at that point they will be deleted. Only the investigator and study personnel will have access to the digital audio recordings in order to compare the ratings on the standardized interview format. Sessions will be recorded digitally. All files will be secured using a digital encryption key. No unauthorized persons will be able to access this key to open the audio files. These encrypted audio files will be de-identified , stored and password protected on a secure server. Any identifying information embedded in the audio recordings will be deleted during the transcription process. Any data sharing will follow all the NYU data security requirements. Identifiable data will not be stored on laptops, PDA's, flash drives or other portable devices. De-identified data will be shared via mailed encrypted CDs, encrypted emails, or via a VPN access and secure access to the secure NYU server.

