A copy of the signed informed consent document will be stored in the subject's research record. The consent process, including the name of the individual obtaining consent, will be thoroughly documented in the subject's research record. Any alteration to the standard consent process (e.g. use of a translator, consent from a legally authorized representative, consent document presented orally, etc.) and the justification for such alteration will likewise be documented.

Patients who consent to participate in the study will also be invited to consent to having their remote and/or inperson screening assessments (i.e. SCID and CAPS) audio-recorded at the initial visit (see Audio Recording Consent) for quality control and for voice-markers analysis. If a patient does not sign the Audio Recording Consent, then we will not audio-record the patient's interview.

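### The lexical part of the Exploratory Aim 1 voice-marker models is built on the interviews that set the diagnosis, so its accuracy is biased upward as evidence of a marker outside those interviews

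*Combined protocol and SAP*

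**What the plan says.** Exploratory Aim 1 (section 3.2, repeated in 4.1) has two parts. The first is to examine voice markers by AUD and PTSD status. The second is to "develop assessment models that use lexical and prosodic features to classify a patient's AUD and PTSD status".

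**Source of the speech.** Section 7.2.4 states: "The study team will collect speech data from audio recordings collected from the clinical interview at the screening visit". Section 23.3.2 names the interviews; participants are asked to agree to have their "screening assessments (i.e. SCID and CAPS) audio-recorded at the initial visit (see Audio Recording Consent) for quality control and for voice-markers analysis".

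**Source of the diagnoses.** Section 7.1 says that the SCID "will be used to determine substance use disorder diagnoses and exclusionary psychiatric disorders". Inclusion criterion 3 in section 5.1 requires a "DSM-5 diagnosis of PTSD with Clinician Administered PTSD Scale (CAPS-5) OR subPTSD diagnosis", the latter also made with the CAPS-5. The section 7.1 text that introduces these instruments goes on to say: "Audio recordings will also be used for voice-marker analysis".

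**What is removed.** Section 7.2.4 plans transcription and says: "Any identifying information embedded in the audio recordings will be deleted during the transcription process". Neither that section nor 4.1 mentions removing anything else.

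**Analysis.** Section 20 contains no voice-marker analysis. Its Exploratory Hypothesis 1 (20.2 and 20.3.10) is a different matter: whether PTSD symptoms improve before drinking does.

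**The concern.** Lexical features are derived from the words spoken. In a SCID or CAPS interview, many of those words are answers to questions about symptoms and drinking, and the rater turns those answers into the diagnosis. A model given the transcript and asked for the diagnosis can therefore succeed by recovering the answers. This is incorporation bias: the predictor contains part of the reference standard.

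What is at stake is the meaning of the result. A high accuracy could be read as evidence that speech carries a marker of AUD or PTSD, when it may show only that a transcript of a diagnostic interview reveals the diagnosis. Such a result need not carry over to speech recorded in any other setting.

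**Working it through.** The documents give no accuracy, sample size or power for the voice-marker models, so there is no figure to reproduce. The check is of design logic, followed by an illustration.

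**Step 1. Trace predictor and label.**

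| Element | What the protocol gives | Section |
|---|---|---|
| Features | Lexical and prosodic | 3.2, 4.1 |
| Speech | Clinical interview at screening | 7.2.4 |
| Interviews recorded | SCID and CAPS | 23.3.2 |
| AUD diagnosis | SCID | 7.1 |
| PTSD or subthreshold PTSD diagnosis | CAPS-5 | 5.1 |
| Content removed | Identifying information only | 4.1, 7.2.4 |
| Other recorded speech | None described | – |

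The chart diagnoses in section 5.4 serve to find candidates. The study diagnoses come from SCID and CAPS, so under the natural reading of status the lexical predictor and the label come from the same conversation.

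**Step 2. Look for a safeguard.** Section 20 defines no label, feature rule, validation scheme or accuracy measure for this aim. Nothing excludes symptom answers or interviewer turns.

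**Step 3. Would cross-validation help?** No. It guards against fitting noise in the training set. Here the overlap lies within each participant: a held-out transcript holds the answers that set that participant's label.

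**Step 4. Separate the feature types.** Prosody (pitch, rate, pauses) does not state a symptom, so it is not circular by content. Interview length and skip pattern could still carry some label information.

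**Step 5. Illustrate direction.** Let d1 be the standardised separation from speech signal that would also exist outside the interview, and d2 the separation from symptom content. For independent normal scores with equal variance, AUC = Φ(√(d1² + d2²)/√2). Both inputs are assumptions. For example, d1 = 0 and d2 = 1 gives Φ(1/1.414) = Φ(0.707) = 0.76.

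| True AUC outside the interview | d2 = 0.5 | d2 = 1 | d2 = 2 | d2 = 3 |
|---|---|---|---|---|
| 0.50 (d1 = 0) | 0.64 | 0.76 | 0.92 | 0.98 |
| 0.64 (d1 = 0.5) | 0.69 | 0.79 | 0.93 | 0.98 |
| 0.76 (d1 = 1) | 0.79 | 0.84 | 0.94 | 0.99 |

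Every entry exceeds its true value; the amount depends wholly on d2.

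**Step 6. Illustrate the cross-validation point.** Three simulations had no independent voice signal: 20 yes/no answers, label positive if at least 6 are present, lexical features equal to the answers recovered correctly with an assumed probability, 100 recordings, and AUC from a 5-fold cross-validated ridge logistic model. The set-ups differed in latent structure and gave about 66%, 68% and 71% positive labels.

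| Answers recovered correctly | 66% positive | 68% positive | 71% positive |
|---|---|---|---|
| 55% | 0.53 | – | – |
| 60% | 0.62 | – | – |
| 65% | 0.72 | – | – |
| 70% | 0.80 | 0.84 | 0.75 |
| 80% | – | 0.94 | 0.87 |
| 90% | – | 0.98 | 0.95 |

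Models on pure noise, standing in for uninformative prosody, gave about 0.48 to 0.50. The leak is an input here, so the tables show only that cross-validation leaves it in place and that its size runs from negligible to near-perfect with the assumed recovery rate. The simulations use a bare symptom count, whereas section 5.1 also requires criteria A, F, G and H for subthreshold PTSD. They do not model the AUD label.

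**The case against.** Several points on the other side have force.

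- **Status is never defined for this aim.** That it means the SCID/CAPS diagnosis is an inference. It is a natural one, since those are the diagnostic instruments described, but the point is conditional on it.
- **The intended use is not stated.** The protocol speaks of assessment models. If the goal were automated scoring of interview speech, symptom content would be a legitimate input and the accuracy would not be inflated for that use. This stands, and it is why the fix keeps lexical models and changes only how they are described.
- **Only portions of interviews may be recorded**, according to the Protocol Summary. The portions are not specified, and section 23.3.2 names SCID and CAPS without exempting any item.
- **A formal SAP is to follow** before database lock (20.1). That is an opportunity to settle the matter; it does not show that it has been settled.
- **The component is exploratory and needs separate consent.** This limits the consequence, but the aim should still yield a result that can be interpreted.

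A reader might go further and infer that all of Exploratory Aim 1 is circular. The documents do not support that: the overlap of content affects the lexical features in the modelling part, not prosody. Nor do they support saying that lexical and prosodic features will be pooled. The text refers to models in the plural and does not say how features are combined.

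**Conclusion.** The point holds for lexical features. If AUD and PTSD status means the SCID and CAPS diagnoses, the accuracy of a lexical model on the recorded interviews is biased upward as evidence of a voice marker for speech outside the diagnostic interview, and cross-validation does not correct it. A combined model inherits the problem through its lexical part.

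The direction follows from the design under that reading of the label and that intended use. The size is unknown: the documents give neither the number of recordings nor how well text features recover answers. A reader might take the AUCs above as forecasts; they are illustrations on assumed values only.

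The consequence is confined to what Exploratory Aim 1 can conclude. No randomised comparison, safety outcome, or primary or secondary endpoint is touched.

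**What to change.** In Exploratory Aim 1 (3.2) and the Voicemarkers Procedure (7.2.3), and carried into the SAP:

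1. State that the label is the SCID diagnosis for AUD and the CAPS-5 diagnosis for PTSD or subthreshold PTSD.
2. Fit and report a prosody-only model on participant speech, with interviewer speech removed, separately from any model that uses lexical features.
3. Base any claim about a voice marker on the prosody-only model.
4. Report lexical or combined models on SCID/CAPS speech as agreement with the interview rating, not as marker accuracy.

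Requiring lexical features to come from speech outside the SCID and CAPS items would not be workable as a wording change, because no such recording is described.

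The cost is protocol and SAP text, analysis work to separate speakers, and probably a less favourable headline accuracy. No new recordings are needed. Section 7.2.4 has the recordings deleted when the study ends, so these rules should be fixed while the audio still exists.

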#### **Re-Contacting Screen Failures**

In the event the protocol inclusion and exclusion criteria are updated, previously screened participants will be reconsidered for inclusion in the study. If a previously screened participant is eligible under the updated inclusion and exclusion criteria, they will be contacted via phone or email to ascertain whether they are still interested in participation. If interested, the participant will be brought in for re-consent and a Clinical Re-Screen or a new Screening Visit if 3 months or greater have passed since the initial screening.

### **Re-Consent**

If the consent is revised (e.g.: new procedures, risk information, compensation, data sharing, etc.), participants will be re-consented with the most updated version of the consent form at their next visit. New information that could substantially affect a participant's desire to continue in the study will be communicated via phone, followed by re-consent at the next study visit.

## 23.4 Participant and Data Confidentiality

Information about study subjects will be kept confidential and managed according to the requirements of the Health Insurance Portability and Accountability Act of 1996 (HIPAA). Those regulations require a signed subject authorization informing the subject of the following:

- · What protected health information (PHI) will be collected from subjects in this study
- · Who will have access to that information and why
- Who will use or disclose that information
- The rights of a research subject to revoke their authorization for use of their PHI.

In the event that a subject revokes authorization to collect or use PHI, the investigator, by regulation, retains

the ability to use all information collected prior to the revocation of subject authorization. For subjects that have revoked authorization to collect or use PHI, attempts should be made to obtain permission to collect at least vital status (i.e. that the subject is alive) at the end of their scheduled study period.

Participant confidentiality is strictly held in trust by the participating investigators, their staff, and the sponsor(s) and their agents. This confidentiality is extended to cover testing of biological samples in addition to the clinical information relating to participants. Therefore, the study protocol, documentation, data, and all other information generated will be held in strict confidence. No information concerning the study or the data will be released to any unauthorized third party without prior written approval of the sponsor.

The study monitor, other authorized representatives of the sponsor, representatives of the IRB or pharmaceutical company supplying study product may inspect all documents and records required to be maintained by the investigator, including but not limited to, medical records (office, clinic, or hospital) and records of drug dispensation for the participants in this study. Records will be housed in a secured space in 1 Park, A, C-D, and H buildings of Bellevue Hospital Center with limited access to study PI and designated study staff only. The clinical study site will permit access to such records.

The study participant's contact information will be securely stored at each clinical site for internal use during the study. At the end of the study, all records will continue to be kept in a secure location for as long a period as dictated by local IRB and Institutional regulations as described in section 24.2.

Study participant research data, which is for purposes of statistical analysis and scientific reporting, will be transmitted to and stored at NYU Langone Medical Center. This will not include the participant's contact or identifying information. Rather, individual participants and their research data will be identified by a unique study identification number. The study data entry and study management systems used by clinical sites and by NYU Langone Medical Center research staff will be secured and password protected. At the end of the study, all study databases will be de-identified and archived at the NYU Langone Medical Center.

Confidentiality of research material will be ensured by storing the research materials in locked cabinets. Material will be available only to project staff, and only as needed. All project staff will be thoroughly trained in issues relating to confidentiality. Participants will be identified in case report forms (CRFs) by initials and an identification code. Data will be entered into TrialMaster™, a program provided by NYU's Datacore designed specifically for clinical trials to protect patient privacy and confidentiality. Published reports will be based on group data; no individual data will be reported.

To further protect the privacy of study participants, a Certificate of Confidentiality will be obtained from the NIH. This certificate protects identifiable research information from forced disclosure. It allows the investigator and others who have access to research records to refuse to disclose identifying information on research participation in any civil, criminal, administrative, legislative, or other proceeding, whether at the federal, state, or local level. By protecting researchers and institutions from being compelled to disclose information that would identify research participants, Certificates of Confidentiality help achieve the research objectives and promote participation in studies by helping assure confidentiality and privacy to participants.

If the study participant has previously participated in a research study at NYU, we will ask the participant's permission to link their previously collected data to the data collected in this research study in order to retain longitudinal information on the participant.

### 23.4.2 Research Use of Stored Human Samples, Specimens, or Data

- Intended Use: Samples and data collected under this protocol may be used to evaluate study eligibility and plasma concentrations of CBD and THC. No genetic testing will be performed.
- Storage: Access to stored samples will be limited by storing samples in a securely locked area. Samples and data will be stored using codes assigned by the investigators. Data will be kept in password-protected computers. Only investigators will have access to the samples and data.
- Tracking: Data will be tracked using paper and electronic logs.
  - Disposition at the completion of the study: All stored samples will be sent to GRM Document Management. Study participants who request destruction of samples will be notified of compliance with such request and all supporting details will be maintained for tracking.

